#### **SYNOPSIS**

**Title of Study:** An Observational Study to evaluate the incidence of clinically suspicious Lambert-Eaton Myasthenic Syndrome (LEMS) in subjects diagnosed with Small Cell Lung Cancer (SCLC)

Investigational sites: Up to 10 investigative sites; USA

Study Phase (if applicable): N/A observational study

#### Study Objectives and Endpoints:

#### **Primary Objective(s):**

 Evaluate the incidence of clinically suspicious LEMS diagnosis in Subjects diagnosed with Small Cell Lung Cancer

#### Secondary Objective(s):

- Correlate the occurrence of clinically suspicious LEMS neurologic symptoms with VGCC antibody positivity.
- Evaluate the occurrence of clinically suspicious LEMS with Small Cell Lung Cancer.
- Evaluate the occurrence of clinically suspicious LEMS with Lung Cancer treatments received.
- Record the number of subjects enrolled with a prior LEMS diagnosis.

#### Study Rationale and Design:

The incidence of LEMS associated with small cell lung cancer (SCLC) is described as about 3%, but population screening has not been evaluated. We hypothesize that the incidence of LEMS associated with SCLC is higher, and a screening test may help to better identify patients. We plan a multi-center testing of as many eligible patients as possible who present to clinic with small cell lung cancer. We will monitor testing every 3 months with documentation of any symptoms. Any workup will be done per standard of care.

#### **Number of Subjects per Cohort:**

Up to 400 subjects with SCLC

#### **Subject Population:**

Adult subjects meeting age of majority (AOM), with a diagnosis of SCLC will be enrolled.

#### Test Product:

N/A Observational Study

Reference Product: N/A

#### **Study Duration:**

Part A (est. 12 months): All subjects enrolled will have quarterly (Q 3 months) visits conducted during this initial 12-month period. At around month 12, enrollment and study visits will be suspended and an interim analysis for futility will be performed to determine if the study will progress into Part B.

Part B: The duration and sample size for Part B will be determined from the Part A interim analysis.

#### Criteria for Evaluation:

All enrolled subjects will be used for evaluation.

Statistical Methods: A descriptive analysis of all data collected will be carried out.

• At 1 year (12 months) an interim analysis for futility will be conducted.

## 1 INTRODUCTION

## 1.1 Background

Lambert-Eaton Myasthenic Syndrome (LEMS) is a rare auto-immune presynaptic disorder of the neuromuscular junction (NMJ) associated with proximal muscle weakness, reduced or absent muscle stretch reflexes, and autonomic dysfunction (PMID: 4330759). Up to 60% of cases occur in the setting of a paraneoplastic disorder, with small-cell lung cancer (SCLC) being the most common tumor type (PMID: 21245427; 2838124; 15277653). Antibodies (Ab) against voltage-gated calcium channels (VGCC), particularly of the P/Q type, are identified in 85-90% of patients with LEMS (PMID: 9668336; 7739683; 9094058). Antibodies to N-type and L-type VGCC have also been reported in 25-40% of LEMS, concurrently with the P/Q-type antibodies, where (PMID: 8309586; 8583238), while few cases are seronegative.

Awareness of the clinical features, diagnostic evaluation, malignancy workup, and management of LEMS, as well as a high index of suspicion, are important for timely diagnosis and proper treatment. When LEMS is suspected or diagnosed, the evaluation of a primary malignancy, particularly SCLC, is warranted due to the strong association. A diagnosis of SCLC has been established within 1 year of LEMS diagnosis in 96% of patients (PMID: 18779614). Treatment of the underlying malignancy may be the only intervention necessary to improve neurologic symptoms.

In the context of LEMS associated with SCLC, the median survival is approximately 18 months. Median survival in individuals with SCLC and LEMS is better than those with only SCLC (median survival of 17 vs 7 months). This longer survival was seen in both limited SCLC (median survival of 19 vs 12.1 months) and extensive SCLC (13 vs 4.9 months). Individuals with non–tumor–associated LEMS have a similar life expectancy to the general population.

#### 1.2 Rationale

LEMS is a paraneoplastic syndrome that occurs in about 3% of individuals with small cell lung cancer, whereas the prevalence of VGCC antibodies at the time of SCLC diagnosis is estimated around 7-8% of patients (**PMID: 15904978; 19934775**). However, the frequency of neurologic symptoms has not been thoroughly evaluated, neither has longitudinal serial assessment of VGCC antibodies throughout the SCLC disease course. This study aims at evaluating the incidence of LEMS in patients with SCLC at the time of their initial diagnosis, as well as at regular timepoints during their disease course.

#### 1.3 Overall Benefit/Risk Assessment

This is an observational, non-treatment, non-interventional, non-randomized multi-center study in subjects who have been diagnosed with Small Cell Lung Cancer. No expected benefit or risk is anticipated for subjects participating in the study.

## 2 STUDY OBJECTIVES

## 2.1 Primary Objective

 To evaluate the incidence of clinically suspicious LEMS diagnosis in small cell lung cancer patients

## 2.2 Secondary Objective(s)

- To correlate the occurrence of clinically suspicious LEMS symptoms with VGCC antibody positivity
- To evaluate the occurrence of clinically suspicious LEMS with SCLC
- To evaluate the occurrence of clinically suspicious LEMS with Lung Cancer treatments received
- Record the number of subjects enrolled with a prior LEMS diagnosis

#### 3 STUDY DESIGN AND EVALUATION

## 3.1 Study Design

This is a multi-center observational study in subjects with a diagnosis of small cell lung cancer. All eligible subjects enrolled will undergo a brief, symptom directed neurological evaluation and VGCC antibody testing (to be performed at a participating Quest laboratory). The results (positive/negative) of VGCC antibody testing will be documented as well as the receptor type P, Q or N.

These tests will be repeated quarterly (Q3 months) for the duration of the study.

If at any visit the subject is found to be BOTH neurologically suggestive of having LEMS and the VGCC Ab test is positive, then the subject is considered to be Clinically Suspicious of having LEMS. At any visit if a subject meets the criteria of Clinically Suspicious of LEMS. the end of study visit will be completed. Once the End of study visit is completed no further treatment information will be collected.

There will be an Investigator Intended Course of Action Form to record possible course(s) of action taken for all subjects who meet the definition of clinically suspicious LEMS (have positive VGCC antibody and suspicious neurologic symptoms). A confirmatory diagnosis of LEMS is by electrophysiologic studies, including repetitive nerve stimulation and/or single fiber electromyography, in patients with suspicious neurologic symptoms and positive VGCC antibodies. This observational (only) trial will not involve any medical course of action as an outcome to testing or participation in this trial, and no adjustments to the subject's existing treatment plan will result as an outcome to participation in this trial. Any treatment actions that

may be considered stemming from participation in this trial will not be considered as part of this observational study – and the intended course(s) of action only will be recorded in this trial. If a subject has been diagnosed with LEMS prior to enrollment in the study, the symptom directed neurological evaluation and VGCC Ab collection do not need to be completed. The enrollment visit and End of study visit will be completed once all diagnosis information has been collected. No further follow up will be needed for this subject.

This study is to be conducted in conformance with the International Conference on Harmonisation/Good Clinical Practices (ICH/GCP).

## 3.1.1 Duration of Study

Part A (est. 12 months): All subjects enrolled will have quarterly (Q 3 months) visits conducted during this initial 12-month period. At around month 12, enrollment and study visits will be suspended and an interim analysis for futility will be performed to determine if the study will progress into Part B.

Part B: The duration and sample size for Part B will be determined during from the Part A interim analysis.

If the interim analysis for Part A determines that Part B will not be conducted, then the study will be closed and all study close out procedures completed.

## 3.1.2 Screening / Enrollment

Potential subjects will be reviewed against the inclusion/exclusion criteria to determine eligibility. Small Cell Lung Cancer treatments received up to 30 days prior to enrollment will be collected.

Subjects will be enrolled once eligibility is confirmed.

#### 3.1.3 Observation Period

The observation period begins at enrollment (day 0). Subjects will be evaluated with a symptom directed neurological evaluation and given an order for a VGCC Ab test to be completed at Quest Laboratory. Both the Symptom directed neurological evaluation and VGCC Ab test will be completed every 3 months while the trial remains open.

At each quarterly observation visit the following will be completed;

- Review of disease progression and current cancer therapy
- Complete the symptom directed neurological evaluation
- VGCC Ab test
  - Results of positive/negative and receptor subtype (P, Q, or N) will be documented.

At month 12 of Part A, enrollment and study visits will be suspended for an interim analysis.

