## 4.3 Data Set Analyses

Descriptive analysis of all data collected will be carried out. The study will explore correlations between all variables – including demographics, medical history, symptom directed neurological evaluation, VGCC Ab results, VGCC Ab subtypes identified, number of subjects enrolled with a prior LEMS diagnosis, number of subjects with an incidence of clinically suspicious LEMS diagnosis, and Intended Course of Investigator Action forms. An incidence of clinically suspicious LEMS diagnosis is defined as neurologic symptoms suggestive of having LEMS and positive VGCC Ab.

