## 7.3.4 VGCC Antibody Blood draw

At each observation visit the subject will be provided an order for a VGCC antibody blood test, to be collected within 15 days of the visit, at the Quest Diagnostic Laboratory of their convenience. Quest will report the lab results to the Investigator. The results of positive or negative and any indicated subtype will be documented for the subject

If a positive result is found the Investigator will review if the subject has a clinically suggestive symptom directed neurological evaluation. If the subject is BOTH neurologically suggestive of having LEMS and the VGCC Ab test is positive, then the subject is considered as Clinically Suspicious of having LEMS and the end of study visit completed.

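### Two antibody tests are ordered, but the protocol records one result labelled P, Q or N and does not say which result, or which combination, makes a subject antibody-positive for the primary endpoint

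*Protocol*

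**What the plan says.** **What is ordered.** Appendix 1 (Quest Lab order) has two lines: 34057, a VGCC RIA with no channel type named, and 93882, a VGCC type N antibody. No line is labelled P, Q or P/Q.

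**What is recorded.** Section 3.1: "The results (positive/negative) of VGCC antibody testing will be documented as well as the receptor type P, Q or N". Section 3.1.3: "Results of positive/negative and receptor subtype (P, Q, or N) will be documented". Section 7.3.4 is looser: "The results of positive or negative and any indicated subtype will be documented for the subject".

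**What counts as a case.** Section 7.3.4: "If the subject is BOTH neurologically suggestive of having LEMS and the VGCC Ab test is positive, then the subject is considered as Clinically Suspicious". Section 4.3 agrees: "An incidence of clinically suspicious LEMS diagnosis is defined as neurologic symptoms suggestive of having LEMS and positive VGCC Ab". Neither sets a condition on subtype. Under Sections 3.1, 7.3.3 and 7.3.5, meeting the definition triggers the End of Study visit.

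**What the background says.** Section 1.1 treats P/Q as one type. It describes VGCC antibodies as "particularly of the P/Q type, are identified in 85-90% of patients with LEMS", and adds: "Antibodies to N-type and L-type VGCC have also been reported in 25-40% of LEMS, concurrently with the P/Q-type antibodies".

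**The concern.** The two ordered tests, the three recorded labels and the single endpoint result do not fit together. One unnamed RIA and one type N test give no visible basis for reporting P apart from Q. No rule says how two results become one when they disagree.

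The gap bears on the primary endpoint and takes effect at the visit. Up to 10 sites must decide whether a discordant pair is positive. If they decide differently, the primary count mixes definitions. A subject counted as positive on type N alone has no later antibody draws or neurological evaluations, so what would have followed cannot be recovered. The Synopsis hypothesises an incidence above about 3%, and an unstated inclusive reading would move the count in that direction. The same count is likely to be before the 12-month futility review (Section 4.3.1).

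**Working it through.** **1. The discordant pair on the form.** Page 2 of the Appendix 2 form, completed when symptoms are judged suggestive, offers two branches:

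| Antibody result on the form | Action on the form |
|---|---|
| Positive | Case; complete End of Study visit |
| Negative | Not complete; next visit in 3 months |

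Take a subject with suggestive symptoms, 34057 negative and 93882 positive. One ordered test is positive and one is negative, so both branches apply. Sections 3.1, 4.3, 7.3.3 and 7.3.4 do not resolve this, because each speaks of one antibody test.

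**2. The protocol's own figure.** Section 4.1 gives up to 400 subjects, 3%, and about 12 cases. 400 × 0.03 = 12.0, which reproduces it. The exact (Clopper-Pearson) 95% interval for 12/400 is 1.56% to 5.18%.

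**3. Effect of one case.** 1/400 = 0.25 percentage points. If k of the 12 expected cases were N-only and the rule excluded them:

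| k | Cases | Estimate | Exact 95% CI |
|---|---|---|---|
| 1 | 11 | 2.75% | 1.38-4.87% |
| 2 | 10 | 2.50% | 1.21-4.55% |
| 4 | 8 | 2.00% | 0.87-3.90% |

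**4. Effect if an inclusive rule adds cases.** The documents give no N-only rate, so the inputs here are assumptions. Let f be the extra positives per draw and s the share of those judged symptom-suggestive. Take five draws (enrollment and months 3, 6, 9 and 12), independent, with no deaths or dropout:

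extra cases = 400 × (1 − (1 − f·s)^5)

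| f | s | Extra cases | Total | Estimate |
|---|---|---|---|---|
| 0.5% | 10% | 1.0 | 13.0 | 3.25% |
| 0.5% | 20% | 2.0 | 14.0 | 3.50% |
| 1% | 10% | 2.0 | 14.0 | 3.50% |
| 1% | 20% | 4.0 | 16.0 | 4.00% |

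Five draws is a maximum. Sections 3.1.1 and 3.1.3 suspend enrollment and visits at about month 12 of Part A, so only the earliest enrollees could reach it in Part A. For any given f and s this is therefore an upper setting.

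**The case against.** The best defence is that P, Q or N is loose shorthand for P/Q and N, and that Section 7.3.4 simply takes whatever subtype the laboratory reports. On that reading the labels need only a wording correction. This is fair for the labels, but it does not supply a rule for a discordant pair.

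A second defence is that the data allow repair. Subtype is documented, the laboratory reports to the investigator, and Section 5.1 promises one-to-one mapping from source to CRF. The CRF page for the antibody result is not shown and may hold a field per test. This partly stands: a result labelled N only could be found and recounted later. Follow-up that ended because of that result could not be restored. For the same reason the rule cannot be left wholly to an analysis plan.

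A third defence is that counting any VGCC antibody is reasonable in a screening study. This stands. Section 1.1 says particularly P/Q, not only P/Q, and the 7-8% prevalence in Section 1.2 is for VGCC antibodies without a subtype. The sentence on N-type antibodies is visibly incomplete. A reader might infer that the endpoint must be limited to P/Q. The documents do not establish that, and no ordered test is labelled P/Q.

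A reader might also compare the chance of ever being falsely antibody-positive with the 12 expected cases. At an assumed 1% per assay over five draws, that chance is 1 − 0.99^5 = 4.9% with one assay and 1 − 0.99^10 = 9.6% with two. The comparison fails because a case also needs suggestive symptoms, and five independent draws is a maximum.

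**Conclusion.** The mismatch is real and lies in the text: two ordered tests, one recorded result, labels that the order does not provide, and no rule for disagreement on a primary endpoint whose occurrence ends observation. It is a gap in the endpoint definition; the arithmetic in Section 4.1 is correct. Each case classified differently is worth 0.25 percentage points. The total is unknown because no N-only rate is given; about 1 to 4 extra cases holds only under the assumptions stated above.

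Two further inferences are not supported. A reader might conclude that borderline results count as positive, but the protocol mentions no borderline category, titre or cut-off, so it is silent on this. A reader might also conclude that an analysis of P against Q is planned. Section 4.3 lists only "VGCC Ab results, VGCC Ab subtypes identified" among the variables to be explored. The point is worth acting on because the correction is cheap and protects a small primary count.

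**What to change.** 1. In Sections 3.1 and 3.1.3, replace the P, Q or N label with one result per ordered code (34057 and 93882), using the laboratory's own name for the antigen. Align Section 7.3.4 and the CRF.
2. For each code, record the numeric value, the cut-off and the draw date where the report prints them.
3. State before enrollment which result, or which combination, defines VGCC antibody positive, both for the endpoint and for the End of Study trigger. Carry the same rule into the two branches of the Appendix 2 form.
4. Report N-only positives with suggestive symptoms on a separate line, and give the count under the alternative rule as a sensitivity result.

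No extra sample is needed. The cost is protocol wording, a few CRF fields copied from a report the site already receives, and one more reporting line. That the report prints a numeric value is an assumption; if it does not, item 2 reduces to the result and draw date.

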#### 3.1.4 Study Administration Structure

Protocol ALCMI-024 is sponsored by ALCMI. The administrative structure of the study is described in Table 4.1 Study Administrative Structure.

**Table 4.1 Study Administrative Structure.** 

Group	Responsibility
Addario Lung Cancer Medical Institute (ALCMI)	Provide scientific direction for the study. Responsible for monitoring the progress of the study, data management, site monitoring, determining the need for modification of the protocol, publishing the results of the study.
Quest Diagnostic Laboratories	Collect, process and report the VGCC Ab test
REDCap Database	Electronic Data Capture for the study, Remote monitoring, and Datasets

## 3.2 Study Population

Adult subjects meeting age of majority with a diagnosis of SCLC will be evaluated for possible participation in the study. A goal of up to 400 SCLC subjects will be enrolled at approximately 10 investigational sites. It is anticipated that each investigational site will enroll approximately 40 SCLC subjects during Part A.

Subjects must meet all of the inclusion criteria and none of the exclusion criteria to be enrolled in the study.

#### 3.3 Criteria for Evaluation

All data collected will be included in the data evaluation.

## 4 STATISTICICS

## 4.1 Sample Size Determination

The total target sample size will be up to 400 subjects. With an estimated 3% incidence of LEMS, which correlates with about 12 subjects to meet the definition of clinically suspicious of LEMS.

## 4.2 Data Set Descriptions

The "observation period" refers to all data collected once the subject is enrolled and has completed at minimum one Symptom directed neurological evaluation and/or one VGCC antibody test. The symptom directed neurological evaluation and VGCC Ab tests will not be completed for any subject enrolled with a prior LEMS diagnosis.

The data sets will consist of all data collected including all results of the symptom directed neurological evaluation and the VGCC antibody tests.

The Intended Course of Action determined by the investigators will also be collected for all subjects who have an incidence of clinically suspicious LEMS diagnosis.

## 4.3 Data Set Analyses

Descriptive analysis of all data collected will be carried out. The study will explore correlations between all variables – including demographics, medical history, symptom directed neurological evaluation, VGCC Ab results, VGCC Ab subtypes identified, number of subjects enrolled with a prior LEMS diagnosis, number of subjects with an incidence of clinically suspicious LEMS diagnosis, and Intended Course of Investigator Action forms. An incidence of clinically suspicious LEMS diagnosis is defined as neurologic symptoms suggestive of having LEMS and positive VGCC Ab.

## 4.3.1 Interim Analysis

At approximately 1 year (12 months) after enrollment start, there will be an interim analysis for futility. After review of the data there will be a determination if the study will close or if Part B of the study will be designed and conducted.

## 4.3.2 Safety Analyses

This study is an observational and blood sample collection study that does not involve treatment safety analyses.

## 5 Data Management

Every effort will be made to ensure that data management practices adhere to international standardization of the following data management procedures.

## 5.1 Database Design and Creation

The REDCap database system will be used for this study. This database will be designed to store the data as recorded in the source and will ensure a one-to-one mapping between the source and the electronic case report form (CRF) stored in the system.

## 5.2 Data Coding

Because this is a non-interventional, no treatment study, data coding is not required.

## 5.3 Data Entry and Verification

The data recorded on the protocol-unique source documents will be verified and entered into the REDCap trial database.

#### 5.4 Data Transfer

Data transfers will be sent to Sponsor or their designee, electronically on a schedule and in a format mutually agreed upon by Sponsor or their designee, and the vendor responsible for the analysis of these data.

#### 5.5 Database Lock

At around 12 months there will be a soft lock of the data for interim analysis. The interim analysis will determine if the study should be terminated or if Part B will be designed and conducted.

On completion of the entire trial (Part A and Part B if it is continued), after data entry is complete and the data has been pronounced clean, the database will be locked and final write access will be removed.

## **6 SUBJECT SELECTION AND DISCONTINUATION**

#### 6.1 Inclusion

Subjects must satisfy the following criteria before being enrolled into the study.

- 1) Adult men or women meeting Age of Majority (AOM) at the time of consent
- Provide voluntary consent to participate in this study, documented via a signed informed Consent Form (ICF)
- 3) Any diagnosis of SCLC
- 4) Willing to provide clinical and medical information related to his/her cancer diagnoses to the study team as required
- 5) Willing to comply with the requirements of the study

